2.3.3. Safety Analysis Set

Safety analyses will be performed using the safety analysis set, which includes all immediate treatment subjects (regardless of study phase) who were administered ATIMP, and all deferred subjects who completed their last baseline assessment during the deferred period prior to treatment. Safety analyses will be performed according to actual treatment received.

2.4. Definition of Subgroups

Descriptive summaries of safety and/or efficacy may be done by considering, but not limited to, the following subgroups:

Table 2: Subgroups

| Subgroup | Definition |
|--|--|
| Age Group | 
 • Adults • Children (<16 years old [United Kingdom] or <18 years old [United States]) |
| Country | 
 • United Kingdom • United States |
| Sex | 
 • Female • Male |
| Baseline mean Retinal sensitivity (meanRS) from static perimetry | 
 • meanRS \leq 10 dB • meanRS $>$ 10 dB |

2.5. Study Day and Relative Day

Study Day 1 refers to the day of ATIMP administration for subjects in the dose escalation phase and dose confirmation phase, as well as immediate treatment subjects in dose expansion phase. For deferred treatment subjects during the deferred period prior to treatment, Study Day 1 refers to the end date of the last baseline visit. For deferred treatment subjects during the post-treatment

period, Study Day 1 refers to the day of ATIMP administration. All efficacy and safety assessments at all visits will be assigned a day relative to this date.

Study day (or relative day) for a visit is defined as:

- Visit date - (date of Study Day 1) +1 day, if the visit date is on or after Study Day 1
- Visit date - date of Study Day 1, if the visit date is before Study Day 1

2.6. Baseline

In general, baseline is defined as the closest visit prior to Study Day 1 and will exclude any screening observations (unless there are no other observations prior to ATIMP administration). However, for efficacy parameters with multiple planned assessments in the baseline window, the arithmetic mean of scheduled baseline visits will be used as the baseline value.

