2. GENERAL ANALYSIS DEFINITIONS

2.1. Visit Windows

The following rules are applied to assign actual visits to analysis visit windows. If a subject has two or more actual visits in 1 visit window, the visit closest to the target day will be used as the protocol visit for that visit window. The additional visit(s) will not be used in the summaries or analyses, but they can be used for determination of clinically important outcomes. If two actual visits are equidistant from the target day within a visit window, the later visit is used. All assignments will be made in chronological order. Once a visit date is assigned to a visit window, it will no longer be used for a later time point. If a visit falls outside of the visit window, then this visit will be assigned to the closest window according to the distance to the target day and visit description, if there is no visit assigned to the visit window.

Table 1: Visit Windows

| Dose Escalation Phase, Pediatric Dose Confirmation Phase, and Immediate Treatment Arms of Expansion Phase | | |
|--|----------------------|-------------------|
| Visit Window Label | Time Interval | Target Day |
| Baseline | -6 Months - Day -1 | < Day 1 |
| Day 1 (ATIMP admin.) | Day 1 | Day 1 |
| Day 2 | Day 2 | Day 2 |
| Day 4 | Day 3 – Day 5 | Day 4 |
| Week 1 | Day 6 – Day 10 | Day 8 |
| Week 2 | Day 11 – Day 21 | Day 15 |
| Week 4 | Day 22 – Day 36 | Day 29 |
| Week 6 | Day 37 – Day 56 | Day 43 |

| Week 9 | Day 57 – Day 72 | Day 64 | |
|---|----------------------|---------------------|------------|
| Week 13 | Day 73 – Day 160 | Day 92 | |
| Week 26 | Day 161 – Day 259 | Day 183 | |
| Week 39 | Day 260 – Day 350 | Day 274 | |
| Week 52 | Day 351 – Day 393 | Day 365 | |
| Deferred Treatment Arms of Expansion Phase | | | |
| Period | Visit Window Label | Time Interval | Target Day |
| Deferred Period (prior to treatment) | Baseline | -6 Months - Day 1 | ≤ Day 1 |
| | Week 13 | Day 73 – Day 168 | Day 92 |
| | Week 26 | Day 169 – Day 365 † | Day 183 |
| Post treatment period | Day 1 (ATIMP admin.) | Day 1 | Day 1¶ |
| | Day 2 | Day 2 | Day 2¶ |
| | Day 4 | Day 3 – Day 5 | Day 4¶ |
| | Week 1 | Day 6 – Day 10 | Day 8¶ |
| | Week 2 | Day 11 – Day 21 | Day 15¶ |
| | Week 4 | Day 22 – Day 36 | Day 29¶ |
| | Week 6 | Day 37 – Day 56 | Day 43¶ |
| | Week 9 | Day 57 – Day 72 | Day 64¶ |
| | Week 13 | Day 73 – Day 160 | Day 92¶ |
| | Week 26 | Day 161 – Day 365 † | Day 183¶ |

¶: after ATIMP administration day for deferred subjects

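### SAP 2.6 ties baseline to Study Day 1 but its screening exception to ATIMP administration, so read literally a screening-only value is a baseline in the immediate arms and not in the control arm

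*SAP*

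**What the plan says.** SAP 2.6 gives a general rule: "baseline is defined as the closest visit prior to Study Day 1 and will exclude any screening observations". It then re-admits screening values under one condition: "unless there are no other observations prior to ATIMP administration". For efficacy measures with several planned baseline assessments it substitutes an average: "the arithmetic mean of scheduled baseline visits will be used as the baseline value".

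SAP 2.5 defines Study Day 1 differently in the two groups being compared. For treated participants, including the immediate arms of the expansion phase, "Study Day 1 refers to the day of ATIMP administration for subjects in the dose escalation phase" and for those later groups too. For controls, "For deferred treatment subjects during the deferred period prior to treatment, Study Day 1 refers to the end date of the last baseline visit".

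The visit-window table in SAP 2.1 also differs by arm. The immediate-arm baseline row ends "6 Months - Day -1 | < Day 1", so Day 1 is out. The control row reads "Deferred Period (prior to treatment) | Baseline | -6 Months - Day 1 | ≤ Day 1", so Day 1 is in.

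Walk time in the maze is a secondary endpoint analysed as change from baseline (SAP 5.4.1), in a model that also has the baseline value as a covariate (SAP 5.4.2). In SAP 5.5 it is tested third, after the perimetry responder endpoint and V30. Microperimetry, the patient-reported outcome, low luminance acuity, contrast sensitivity and EZ area are tested only if it succeeds.

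**The concern.** The rule and its exception run on different clocks. In the immediate arms the clocks coincide. In the control arm they are about six months apart, and the two main control-period visits fall in the gap. One sentence can therefore give a baseline in one arm and none in the other, from the same kind of data.

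The endpoint most exposed is the maze. Without a control baseline there is no change score and no covariate, so the third test in the sequence cannot be run and the later endpoints cannot be reached as planned. In practice someone would choose a baseline at the programming stage. SAP 1.4 says sponsor and site personnel were not masked. SAP 3 describes an interim summary of efficacy at a cutoff of 2 November 2020, about a year before the approval date of 16 November 2021 printed in the SAP. A gatekeeping endpoint should not depend on a choice made at that point.

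**Working it through.** The documents state no figure to reproduce. The check applies SAP 2.5 and 2.6 literally to the assessment schedule.

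**Inputs**
- Arm sizes: up to 16 low dose + 16 intermediate dose = 32 immediate, and up to 16 deferred (protocol 5.9.1).
- Maze schedule: protocol Tables 3 and 4, in the available text, show a mark at screening and none in the baseline columns. Table 4 then shows Month 3 and Month 6 before ATIMP, and Months 3 and 6 after it.
- Timing: Table 4 footnote 8 places Months 3 and 6 after the last baseline visit; ATIMP follows the Month 6 assessments.
- Supporting text: protocol 5.3.1.6.2 lists the maze as a screening test. Protocol 5.3.1.6.4 exempts it from the tests repeated when ATIMP is delayed beyond 3 months.
- Questionnaires: one baseline mark in Table 4. Footnote 1 allows all baselines on one day.

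**Maze, immediate arms.** Study Day 1 is ATIMP. The only earlier maze result is screening. Nothing else precedes ATIMP, so the exception applies and screening is the baseline: up to 32 of 32.

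**Maze, control arm.** Count days from the last baseline visit, with illustrative dates: screening at about -90, Month 3 at 91, Month 6 at 182, ATIMP at about 190.
1. Non-screening values before Study Day 1: none.
2. Exception: are there other observations before ATIMP? Yes, at days 91 and 182. The exception fails.
3. Screening stays excluded, so there is no baseline: 0 of up to 16.

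The averaging rule does not help, because it needs several planned baseline assessments. The specific maze imputation in SAP 5.4.2 covers participants who refuse or cannot navigate the maze, not values removed by a definition.

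**Single-baseline measures, control arm.**

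| Baseline visits | SAP 2.6 (before Day 1) | SAP 2.1 (Day 1 or earlier) |
|---|---|---|
| On separate days, measure taken before the last | kept | kept |
| All on one day | lost | kept |

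The immediate arms keep the value in both cases. The measures concerned include the questionnaires; the IVI reading domain has its own alpha of 0.01 in SAP 5.5.

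**Repeated-baseline measures.** Static perimetry (the responder endpoint and V30), microperimetry, low luminance acuity, contrast sensitivity and OCT have three baseline marks in Table 4. The averaging rule gives a baseline in both arms.

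**Age of a screening value.** Screening may precede randomisation by up to 4 months. If the baseline period starts at randomisation, Study Day 1 can be 3 months later (main text and Table 3) or 4 months later (Table 4 footnote 1). That is 4 + 3 = 7 or 4 + 4 = 8 months, against a window that opens at 6. The closest-window rule in SAP 2.1 may recover such a value, but SAP 2.6 does not say so.

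**The case against.** The strongest objection is that the maze may not be screening-only. Protocol 5.4.2.1 lists visual mobility among the baseline tests for all participants, and the footnotes to Tables 3 and 4 make tests so listed mandatory. In the available text the tables have visibly lost marks: informed consent has none in Table 3, and PCR has no baseline mark there although protocol 5.4.2.3 requires one. An empty cell is therefore weak evidence. The SAP also follows protocol v12.0, while the supplied protocol's amendment table ends at v11.0. This stands. If a maze test was done before the last baseline visit, the maze loss disappears; if it was done on that day, only the Day 1 inconsistency remains.

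The second objection is that the literal reading is strained. SAP 2.1 assigns the Month 3 and Month 6 visits to the Week 13 and Week 26 windows, and SAP 2.3.2 treats such visits as post-baseline. A sensible programmer would take the other observations to mean other candidate baselines and use screening in both arms. That is probably the intent, but the sentence names ATIMP, so reaching that result means departing from it.

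The third objection is that the Day 1 problem is narrow. It is: protocol 5.4.2.1 prefers separate days for repeated tests, the window table already keeps the value, and the documents give no count of one-day baselines.

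A reader might infer that the rule strips controls of their baselines generally, or that the maze comparison is certainly lost. The documents support neither. The averaging rule covers most of the efficacy measures, including the primary, and the maze loss depends on the schedule actually followed.

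**Conclusion.** The defect in wording is certain: SAP 2.6 ties its exception to ATIMP administration when it should be tied to Study Day 1, and it disagrees with SAP 2.1 on whether Day 1 counts in the control arm. The first of these treats the two compared arms differently.

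The consequence is conditional. Up to 16 of 16 controls lack a walk-time baseline only if the maze was done at screening and not at baseline, and the rule is applied to the letter. The Day 1 inconsistency reaches only single-baseline measures taken on the last baseline day, in an unknown number of controls.

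The primary analysis and V30 are not affected. The point still merits correction, because it sits at a gate in the alpha-controlled sequence and the correction works whichever schedule was followed.

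**What to change.** In SAP 2.6, replace the general rule with wording such as:

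> *Baseline is the last value on or before Study Day 1 of the relevant period (pre-dose for treated periods). A screening value is used when no other value exists on or before Study Day 1.*

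Then:
- Keep the averaging rule for measures with repeated baselines.
- Use the same wording in the SAP 2.1 visit-window table.
- Name the maze baseline explicitly, identically for both arms, and reconcile protocol 5.4.2.1 with Tables 3 and 4.
- State that a screening value used in this way is accepted even if it falls before the 6-month window.

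If the maze was screening-only, usable control baselines go from 0 to up to 16 of 16, the immediate arms stay at up to 32 of 32, and the comparison can be estimated. If a baseline maze exists, the new wording selects it. The cost is a few lines of SAP text and one programming check, listing the baseline source for every participant and endpoint by arm.

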2.7. Imputation Rules for Missing AE Date and Resolution

Partial adverse event (AE) onset dates will be imputed as follows:

- If the onset date of an AE is only missing the day, it will be imputed as:
 - First day of the month that the AE occurred, if month/year of the onset of the AE is different than the month/year of ATIMP administration
 - The day of ATIMP administration, if the month/year of the onset of AE is the same as month/year of ATIMP administration and month/year of the AE resolution date is different
 - The day of ATIMP administration or day of AE resolution date, whichever is earliest, if month/year of the onset of AE and month/year of ATIMP administration and month/year of the AE resolution date are same
- If the onset date of an AE is missing both day and month, it will be imputed to the earliest of:
 - January 1 of the year of onset, as long as this date is on or after ATIMP administration
 - Month and day of ATIMP administration, if this date is the same year that the AE occurred
 - Last day of the year if the year of the AE onset is prior to the year of ATIMP administration,
 - The AE resolution date.
- Completely missing onset dates will not be imputed.

Partial AE resolution dates not marked as ongoing will be imputed as follows:

- If the resolution date of an AE is missing day only, it will be set to the earliest of the last day of the month of occurrence of resolution or the day of the date of death, if the death occurred in that month.

- If the resolution date of an AE is missing both day and month, it will be set to the earliest of December 31 of the year or the day and month of the date of death, if the death occurred in that year.

Completely missing resolution dates will not be imputed.

3. ADMINISTRATIVE INTERIM ANALYSIS

An administrative interim analysis was conducted summarizing both safety and efficacy endpoints to help plan Phase 3 study (MGT-RPGR-021) on data cutoff date 02NOV2020. All available data (including visits after 6 months and up to 12 months for subjects enrolled earlier) were used for this interim analysis. Given the administrative nature of this interim analyses which is intended to support subsequent planning, there is no impact to type I error rate. Results of primary and secondary efficacy endpoints as well as key safety analyses were summarized.

4. SUBJECT INFORMATION

The number of subjects in each analysis set will be summarized by treatment group and overall. In addition, the distribution of subjects by country and site will be presented unless otherwise noted.

4.1. Demographics and Baseline Characteristics

[Table 3](#) list the demographic and baseline characteristic variables that will be summarized by study Phase, treatment group and overall for the Safety Analysis Set and All Enrolled Analysis set, respectively.

Table 3: Demographic Variables and Baseline Characteristics

| Continuous Variables: | Summary Type |
|-------------------------------------|---|
| Age (years) | Descriptive statistics (N, mean, SD, median and range [minimum and maximum]). |
| Weight (kg) | |
| Height (cm) | |
| Categorical Variables | |
| Age group (adult, pediatric) | |
| Sex (male, female) | |
| Baseline meanRS (<= 10 dB, > 10 dB) | Frequency distribution with the number and percentage of subjects in each category. |
| Race | |

^a If multiple race categories are indicated, the Race is recorded as 'Multiple'.

4.2. Disposition Information

A subject will be considered to have completed the study if the subject completes the Week 52 visit.

The number of subjects in the following disposition categories will be summarized throughout the study by age group, treatment group and overall, for the All Enrolled Analysis Set.

- Subjects who were administered ATIMP

- Subjects who completed the study
- Subjects who prematurely discontinued from the study and their reasons for discontinuation

Listings will also be provided.

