4.3.1 Separate longer term follow up study

Safety will be assessed in this study for 12 months following ATIMP administration (6 months for patients in the deferred arm). Participants will be invited to enrol in a separate subsequent follow-up study where they will be assessed for safety up to 60 months following ATIMP administration. The duration of longterm follow-up is therefore consistent with the recommendations of the current CHMP Guideline on Follow-up of **Patients** Administered with Gene Therapy Medicinal Products (EMEA/CHMP/GTWP/60436/2007) of 22 October 2009, where it is stated that, for viral vectors without integration, latency or reactivation potential, a brief clinical history and sample testing should be performed pre-treatment, at 3, 6, 9 and 12 months after treatment, and then yearly thereafter for a minimum of 5 years (and, if non-clinical tests or evidence from other clinical trials using identical vectors or modifications of vectors indicate a potential for integration or late re-activation, the monitoring should be extended to continue yearly after those 5 years until data indicate that there is no longer any risk to be followed). Further, although the FDA Guidance February 2020 (Long Term Follow-up After Administration of Human Gene Therapy Products: Guidance for Industry) recommends a standard 15-year period of follow-up, it is also noted that a shorter period of follow up may be appropriate if the ATIMP does not integrate and has no potential for latency and reactivation.

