1.4. Randomization and Blinding

In dose escalation phase, up to 18 adult participants will be administered one of 3 different doses of the ATIMP in cohorts of 3 participants at a time. Based on toxicity data, the IDMC will make a recommendation on the dose to administer to the next cohort of 3 participants.

Once an acceptable safety profile has been established in adults, the IDMC will agree the maximum tolerated dose in adults, which will be confirmed in 3 pediatric participants.

In the expansion phase, up to 48 subjects were randomized to 1 of 3 arms in a 1:1:1 ratio (Immediate low dose administration: Immediate intermediate dose administration: deferred administration). Subjects randomized to the deferred administration group were further randomized to receive the low or intermediate dose in a 1:1 ratio. The eye selected for administration was also randomized at the start of the expansion cohort. All aspects of randomization occurred on completion of screening. The three treatment groups of the randomized expansion phase will be stratified by age at date of informed consent (<25 years, \geq 25 years) to balance for disease severity between treatment groups with age used as a surrogate for severity.

Visual function assessors and reading centers are masked to treatment (dose levels and immediate vs. deferred treatment). Neither study site nor sponsor personnel were masked to treatment.

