 † : Any scheduled visits after week 26 in deferred treatment arm will be summarized as week 26 visits given COVID-19 delays

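### SAP 4.2 ties study completion to a Week 52 visit that the SAP's visit windows do not give the deferred arm, so read literally no deferred participant can be counted as a completer

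*SAP*

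**What the plan says.** SAP 4.2 (Disposition Information) gives a single rule with no variant by arm: "A subject will be considered to have completed the study if the subject completes the Week 52 visit". It then tabulates subjects who received the vector, subjects who completed, and subjects who discontinued prematurely with reasons. The table is by age group, treatment group and overall, in the All Enrolled Analysis Set. Under SAP 2.3.1 that set contains everyone assigned to a treatment group, so it includes the deferred arm.

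SAP 2.1 (Visit Windows) is the only place where the SAP defines Week 52. For the escalation, paediatric confirmation and immediate arms the last row is "Week 52 | Day 351 – Day 393 | Day 365". For the deferred arm the last row, in the post-treatment period, is "Week 26 | Day 161 – Day 365 † | Day 183". The footnote to the deferred windows adds: "Any scheduled visits after week 26 in deferred treatment arm will be summarized as week 26 visits given COVID-19 delays".

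SAP 2.5 sets Study Day 1 for deferred participants at the end of their last baseline visit during the deferral period, and resets it to the day of vector administration for the post-treatment period. It adds: "All efficacy and safety assessments at all visits will be assigned a day relative to this date".

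Protocol 4.3.1 states: "Safety will be assessed in this study for 12 months following ATIMP administration (6 months for patients in the deferred arm". Protocol Table 4 accordingly ends the deferred schedule at month 6 after administration, Visit 16.

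**The concern.** The completion rule depends on a visit label that one of the three randomised groups never receives. A programmer who derives completion from the SAP's analysis visits would find no Week 52 record for any deferred participant, however complete the follow-up.

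The deferred arm is the concurrent randomised control for the efficacy comparison, and the disposition table is where a reader looks first to judge follow-up by arm. A completion row showing none in the control group would be wrong. The table would also fail to reconcile: deferred participants who attended every visit would appear under neither completion nor premature discontinuation.

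**Working it through.** **1. Size of the deferred arm.** SAP 1.4 says "up to 48 subjects were randomized to 1 of 3 arms in a 1:1:1 ratio". Protocol 5.9.1 gives the overall ratio as 2:2:1:1 (immediate low, immediate intermediate, deferred low, deferred intermediate).

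- 48 × 2/6 = 16 and 48 × 1/6 = 8, so the groups are 16, 16, 8 and 8. This reproduces the protocol's own figures.
- Deferred arm: 8 + 8 = 16.
- Total planned enrolment (Protocol 5.7): 18 + 5 + 48 = 71, which also reproduces.

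**2. Can a deferred participant have a Week 52 visit under the SAP's labels?**

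- Deferral-period windows: Baseline, Week 13 and Week 26. No Week 52.
- Post-treatment windows: Day 1 to Week 26. No Week 39 or Week 52.
- The Week 26 window runs to Day 365 in each deferred period, and the footnote sends later scheduled visits to Week 26. A late visit therefore stays at Week 26.
- Study day restarts at administration, so time before and after treatment does not add up to a Week 52 label.
- A visit 12 months after treatment is not in this study for the deferred arm. Protocol 4.3.1 places it in the separate follow-up study, for the deferred group only.

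The number of deferred participants who can meet the rule is 0 of 16.

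**3. Consequence for the table, with perfect retention.**

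| Group | Planned maximum | Can be counted as completers under the literal rule | Can be counted if completion follows each arm's last scheduled visit |
|---|---|---|---|
| Deferred | 16 | 0 | 16 |
| All randomised | 48 | 48 − 16 = 32 (66.7%) | 48 |
| All enrolled | 71 | 71 − 16 = 55 (77.5%) | 71 |

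The deferred arm is 16/48 = 33.3% of those randomised and 16/71 = 22.5% of those enrolled.

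**4. Would a calendar reading work instead?** Suppose Week 52 meant 12 months from the deferred arm's own Day 1, using the Day 351 to 393 window. A participant treated on deferral day X who attends the post-treatment Week 26 visit on its target, Day 183, finishes on calendar day X + 183 − 1 = X + 182.

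- Treated on the nominal day, X = 183: 183 + 182 = 365, inside the window.
- Upper limit: X + 182 ≤ 393 gives X ≤ 211, which is 211 − 183 = 28 days after the nominal day.

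A participant treated more than 28 days late would finish outside that window even with every visit attended on target. SAP 1.2 reports that treatment in this arm was in fact delayed beyond the planned 6 months, and the deferral-period Week 26 window extends to Day 365.

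**The case against.** The best defence is that Week 52 in SAP 4.2 is shorthand for the end-of-study visit at month 12, which both arms have. Protocol 5.4.2.1 (Treatment Experience Interview) gives the last visit of both the immediate and the deferred groups the label month 12, Visit 16. Protocol Figure 2 shows follow-up complete at 12 months, and SAP 1.2 has deferred participants moving to the long-term study at a 12-month time point. The window rules in SAP 2.1 concern summaries and analyses, and neither they nor SAP 4.2 say that completion is derived from those windows. The programming rule may also sit in the separate Data Presentation Specifications, which are not available here. Finally, the SAP is written to protocol v12.0, whereas the supplied protocol's amendment list ends at v11.0.

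Much of this stands as evidence of what may have been intended. It does not supply the missing rule. SAP 2.1 is the only definition of Week 52 in the SAP, and it calls the deferred arm's final visit post-treatment Week 26. The protocol's naming is not uniform either: the last footnote to Table 4 calls the same visit month 6, Visit 16. A calendar rule would also handle delayed deferred participants badly, as the working shows. If the calendar meaning was intended, the SAP still has to say so.

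The defence is right about harm. A reader might infer that the controls would appear as dropouts, or that retention would look differential between arms. The documents do not support that: SAP 4.2 reports premature discontinuation separately, with reasons, and nothing there puts a fully followed deferred participant in that category. Real dropout would still be visible.

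**Conclusion.** The point holds as a defect in disposition reporting. Read literally, SAP 4.2 allows no deferred participant, up to 16 of 48 randomised or 16 of 71 overall, to be counted as having completed the study, and it leaves fully followed deferred participants in neither outcome category.

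This rests on three assumptions: that completion is derived from the SAP's own visit labels; that no arm-specific rule exists in the Data Presentation Specifications; and that the deferred schedule in the protocol version the SAP implements matches the one supplied. The counts are planned maxima, not actual enrolment, so they give the number who could be affected and do not show that 16 people have been misclassified.

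A reader might also infer that the efficacy or safety results are affected. They are not. The analysis sets (SAP 2.3), the responder denominator (SAP 5.3.1), the mixed models (SAP 5.4.2) and the safety proportions (SAP 6) do not use completion status. This is a minor point, worth correcting because it concerns the control arm and costs almost nothing.

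**What to change.** Replace the sentence in SAP 4.2 with a definition by each arm's last scheduled visit: Week 52 for escalation, paediatric confirmation and immediate-treatment participants, and post-treatment Week 26 (Visit 16) for deferred participants. Carry the same rule into the Data Presentation Specifications if it is not already there.

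As an option, add a disposition line for completion of the 26-week deferral period. That is the follow-up most relevant to the randomised comparison, but the line is an addition and not part of the correction.

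Reconcile Protocol 5.6.3 at the same time: it ends the trial for each participant 12 months after administration, whereas Protocol 4.3.1 and Table 4 give the deferred arm 6 months.

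The cost is one SAP sentence, plus one table row if the option is taken. No new data are needed.
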